## 11.3. Analysis Sets

## 11.3.1. Efficacy Analysis Sets for Part A

For Part A, the full analysis set (FAS) includes all randomized patients in Part A; it is based on the treatment allocated (as randomized). Efficacy endpoints in Part A (double-blind treatment period) will be analyzed using the FAS.

## 11.3.2. Safety Analysis Set for Part A

For Part A, the safety analysis set (SAF) includes all randomized patients who received any Part A study drug; it is based on the treatment received (as treated). Treatment compliance/administration and all clinical safety variables will be analyzed using the SAF.

## 11.3.3. Analysis Set for Parts B and C

For efficacy and safety analyses of Parts B and C, only a subset of SAF for Part A will be included, which is defined as those patients who received at least 1 dose of Part B or/and Part C study drug.

## 11.3.4. Pharmacokinetic Analysis Sets for All Parts

The PK analysis population includes all patients who received any study drug and who had at least 1 non-missing result following the first dose of study drug.

## 11.3.5. Immunogenicity Analysis Sets for All Parts

The ADA analysis set includes all patients who received any study drug and had at least 1 nonmissing ADA result following the first study dose.

The NAb analysis set includes all patients who received any study drug and who are negative in the ADA assay or with at least 1 non-missing result in the NAb assay (patients who are ADA-negative are set to negative in the NAb analysis set).

# 11.4. Statistical Methods

For continuous variables, descriptive statistics will include the following information: the number of patients reflected in the calculation (n), mean, standard deviation, Q1, median, Q3, minimum, and maximum.

For categorical or ordinal data, frequencies and percentages will be displayed for each category.

#### 11.4.1. Patient Disposition

The following will be provided:

- The total number of screened patients who have signed the ICF
- The total number of randomized patients: received a randomization number
- The total number of patients who discontinued the study, and the reasons for discontinuation
- The total number of patients who discontinued from study treatment, and the reasons for discontinuation

## 11.4.2. Demography and Baseline Characteristics

Demographic and baseline characteristics will be summarized descriptively by treatment group, and by all patients combined.

#### 11.4.3. Efficacy Analyses

#### 11.4.3.1. Primary Efficacy Analysis

The primary analysis of proportion of patients achieving a histologic response of peak esophageal intraepithelial eosinophil count  $\leq 6 \text{ eos/hpf}$  at week 16 will be analyzed using the Cochran-Mantel-Haenszel (CMH) test to assess the difference in the proportion of responders in the FAS, adjusting for the randomization stratification factor (baseline weight group). The randomization stratification of baseline weight group may be pooled to ensure the sufficient sample size of each stratum.

For the primary estimands of interest for the primary endpoint, the intercurrent events, strategies, and the corresponding missing data handling approaches are provided as below:

	Estimands				
Endpoint Category	Endpoint(s)	Population	Intercurrent event(s) strategy and missing data handling	Population-level summary/Analysis	
Primary Endpoint	Proportion of patients achieving peak esophageal intraepithelial eosinophil count of ≤6 eos/hpf (400×) at week 16	FAS	
 
The intercurrent events will be handled as follows:
 
Treatment discontinuation: data collected after the patient discontinued treatment will be included in the analysis (Treatment policy strategy)
 
Initiation of treatment with systemic and/or swallowed topical corticosteroids drugs: patients will be considered as non-responders after such event (composite variable strategy)
 
Note: the composite strategy will be considered if a patient receives rescue medication any time during the study.
 
Missing data handling: patients with a missing value for the primary endpoint at week 16 due to study discontinuation or other reasons will be considered to be non-responders
 
	Cochran-Mantel-Haenszel (CMH) test adjusting for the randomization stratification factor (baseline weight group) will be utilized. The estimated proportion of the treatment difference between dupilumab groups and placebo, and its 2-sided 95% confidence intervals will be provided based on the CMH test.	

Sensitivity analyses will assess alternative methods to impute missing data. The sensitivity analyses will include tipping point analysis approach and worst observation carried forward – multiple imputation (WOCF-MI) approach.

Subgroup analyses (eg, by weight) may be performed. Details will be specified in the SAP.

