# CONFIDENTIAL

	Patients are required to have a documented diagnosis of EoE that may be established either by a prior historical biopsy, as demonstrated by intraepithelial eosinophilic infiltration (peak eosinophils/high power field $\geq 15 \text{ eos/hpf}$ ) (400×) from at least 1 esophageal region and performed after at least 8 weeks of treatment with an approved proton pump inhibitor (PPI) regimen, or by biopsies performed after approximately 8 weeks of PPI treatment initiated prior to screening or during the screening period, which demonstrates $\geq 15 \text{ eos/hpf}$ ) (400×) from at least 2 of the 3 esophageal regions (proximal, mid, and distal). Patients who are on PPIs during the screening period to rule out EoE disease management with this treatment, and are eligible to enroll in the study, have the choice either to remain on the PPI regimen during the entire study or stop the PPI regimen prior to baseline (vicit 3); they then must remain off of
	PPIs during the entire study. Biopsies will be obtained by endoscopy at screening visit 2, the week 16 visit, the week 52 visit, the week 100 visit, the week 160 visit, or immediately prior to start of rescue medication or procedures (only applies to rescue medication and/or procedures that occur before the week 52 visit). A total of at least 9 mucosal pinch biopsies will be collected at each time point from 3 esophageal regions: 3 proximal, 3 mid, and 3 distal. Two samples from each region will be used for histology (needed for study inclusion criteria, as well as endpoint assessment) and the other for RNA extraction.
	Patients may receive concomitant medications (except for prohibited medications specified in the protocol body) as needed, at the discretion of the investigator, while continuing study treatment. Frequency of use and type of product will be documented.
	Efficacy, safety, laboratory assessments, and samples for assay of concentration of functional dupilumab in serum and potential anti-drug antibody (ADA) response to dupilumab, as well as research samples, will be performed or collected at specified time points throughout the study according to Schedule of Events specified in the protocol body.
Study Duration	The duration of the study for a patient is up to 172 weeks, excluding the screening period.

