#### Analysis Methods:

#### Primary Efficacy Analysis in Part A

The primary analysis of proportion of patients achieving a histologic response of peak esophageal intraepithelial eosinophil count  $\leq 6 \operatorname{eos/hpf} at$ 

week 16 will be analyzed using the Cochran-Mantel-Haenszel (CMH) test to assess the difference in the proportion of responders in the full analysis set (FAS), adjusting for the randomization stratification factor (baseline weight group). The randomization stratification of baseline weight group may be pooled to ensure the sufficient sample size of each stratum.

To account for use of rescue treatment, patients will be considered as non-responder after rescue treatment.

If a patient has missing value for the histological response (peak esophageal intraepithelial eosinophil count  $\leq 6 \text{ eos/hpf}$ ) at week 16, the patient will be classified as a non-responder at week 16.

Sensitivity analyses will assess alternative methods to impute missing data. The sensitivity analyses will include a tipping point analysis approach and a worst observation carried forward -Multiple Imputation (WOCF-MI) approach.

Subgroup analyses (eg, by weight) may be performed. Details will be specified in the SAP.

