# 6.2. Planned Interim Analysis

No interim analysis is planned for this study.

The primary analysis may be performed once all patients in the study have completed the 16-week double-blind treatment period in Part A as specified in the protocol (week 16 visit or earlier for those patients who are withdrawn prematurely from the study). If performed, this primary analysis will be considered the final analysis for the primary and week 16 secondary efficacy endpoints. A description of the statistical methods to be employed and blinding implications are in Section 11.

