# 8.3. **Rescue Treatments and Procedures**

If medically necessary (eg, for treatment of intolerable EoE symptoms), rescue medications (systemic and/or swallowed topical corticosteroids) or emergency esophageal dilation are allowed for study patients. For Parts A and B, an endoscopy with biopsy will be performed prior to the initiation of rescue therapy. Patients who undergo an endoscopy with biopsy due to the initiation of rescue therapy during Parts A or B will not undergo the subsequent scheduled endoscopy/biopsy at week 16 and/or week 52, respectively. Patients who receive rescue treatment during the double-blind period of the study will not be eligible for the extended active treatment period unless an endoscopy with biopsy is performed prior to the initiation of rescue treatment is also allowed. If rescue therapy is initiated during Part C (OLE), an endoscopy/biopsy before initiating rescue treatment is at discretion of the investigator discretion; future endoscopies/biopsies (week 100 and week 160) would still be required. If the endoscopy with biopsies cannot occur due to COVID-19 restrictions, rescue treatment should be initiated without delay and these patients will be eligible to participate in Part C.

Regeneron Pharmaceuticals, Inc.

Patients receiving rescue therapy may continue to receive study drug. They will remain blinded and will be asked to return to the clinic for all remaining study visits for the double-blind treatment period and the follow-up period, and participate in all assessments for these visits according to the Schedule of Events specified in Table 1, Table 2, Table 3, and Table 4 except for endoscopy/biopsy, as noted above. For the purpose of efficacy analyses for Part A, patients who receive rescue treatment during the study will be considered treatment failures.

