## 11.4.3.2. Secondary Efficacy Analysis

Efficacy Endpoints at Week 16 (Part A)

Secondary efficacy endpoints that measure binary responses (eg, peak esophageal intraepithelial eosinophil count <15 eos/hpf) will be analyzed in the same fashion as the primary endpoint.

Continuous secondary efficacy endpoints will be analyzed using an analysis of covariance (ANCOVA) model for the FAS with treatment group, randomization stratification factor, and relevant baseline measurement as a covariate included in the model.

Regeneron Pharmaceuticals, Inc.
To account for use of rescue treatment, data will be set to missing for all time points subsequent to the use of rescue treatment.

For continuous efficacy data that are scheduled to be measured repeatedly post-baseline up to week 16 (eg, change in the proportion of days with 1 or more EoE signs from baseline to week 16 as measured by PESQ-C), missing data will be imputed by the pattern-mixture approach. Specifically, the WOCF-Multiple Imputation (WOCF-MI) approach, where the WOCF approach will be used for the missing data due to rescue treatment/AE/lack of efficacy and the MI approach will be used for the missing due to other reasons.

For continuous efficacy data that are scheduled to be measured only once post-baseline up to week 16, missing values at week 16 will be imputed with patient's baseline value or the available post-baseline value, whichever is worse, ie, a WOCF approach.

The primary analysis of EoE-EREFS will be based on centralized readings.

For transcriptome endpoints, the Wilcoxon rank-sum test will be used to test if the difference in median NES of the relative change from baseline to week 16 between the dupilumab and placebo groups is statistically significant. P-values will be reported.

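### Section 8.3 makes rescue at any point in the study a Part A treatment failure, while the other rescue rules act only on assessments after rescue

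*Protocol*

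**What the plan says.** The primary endpoint is a peak count of 6 eos/hpf or fewer at week 16, the end of the double-blind period (Part A). The protocol states the effect of rescue on that endpoint in several places.

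**Without a Part A limit on when rescue occurs**
- Section 8.3: "For the purpose of efficacy analyses for Part A, patients who receive rescue treatment during the study will be considered treatment failures".
- Section 11.4.3.1, Note in the estimand table: "Note: the composite strategy will be considered if a patient receives rescue medication any time during the study".

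**Acting only from rescue onward**
- Synopsis, primary efficacy analysis: "To account for use of rescue treatment, patients will be considered as non-responder after rescue treatment".
- Section 11.4.3.1, the bullet directly above the Note: "patients will be considered as non-responders after such event (composite variable strategy".
- Section 11.4.3.2: for continuous endpoints, values at time points after rescue are set to missing.

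Three other statements bear on the reading. Section 8.3 names the double-blind period when it means Part A: "Patients who receive rescue treatment during the double-blind period of the study will not be eligible". It also provides for rescue in Parts B and C. Under Section 11.4.3.2 the binary secondary endpoints "will be analyzed in the same fashion as the primary endpoint". On timing, Section 6.2 says: "The primary analysis may be performed once all patients in the study have completed the 16-week double-blind treatment period in Part A".

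**The concern.** An estimand should give each child one week-16 status. Consider a child with 6 eos/hpf or fewer at week 16 who enters Part B and is first rescued there. Under the synopsis and the estimand bullet the week-16 response stands. Under the Section 8.3 sentence as written, the child is a treatment failure for Part A. Two analysts could each cite the protocol and code this child differently on the primary endpoint and on the binary secondary endpoints.

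The literal rule would also let events outside the randomised comparison change the week-16 result. All patients receive dupilumab in Part B (Section 8.1). With staggered enrolment, early enrollees can be well into Part B when the last patient reaches week 16, while late enrollees have no Part B follow-up. Week-16 status would then depend partly on enrolment date and data cut.

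The split would also fall within one biopsy. For this child the week-16 count would be used in full for percent change in eosinophil count, but be scored as failure at both the 6 and the 15 eos/hpf thresholds.

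**Working it through.** **Step 1. Apply each wording to two kinds of patient.**

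| Text | Rescued before the week-16 biopsy | Week-16 responder, first rescued in Part B |
|---|---|---|
| Synopsis | non-responder | responder |
| 11.4.3.1 bullet | non-responder | responder |
| 11.4.3.1 Note, read with its bullet | non-responder | responder |
| 11.4.3.1 Note, read alone | non-responder | non-responder |
| 8.3 sentence, literal | failure | failure |
| 11.4.3.2, continuous endpoints | week-16 value set to missing | week-16 value used |

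Only the last column is in dispute. The firm conflict is the Section 8.3 sentence; the Note is ambiguous.

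**Step 2. Size per child.** Section 11.2 plans 30 per arm, with 5.1% response on placebo and 40.7% on each dupilumab regimen, a difference of 35.6 points.
- Expected responders: 30 × 0.407 = 12.2 per dupilumab arm; 30 × 0.051 = 1.5 on placebo.
- One child: 1/30 = 3.3 points.
- One dupilumab responder reclassified: 35.6 − 3.3 = 32.3 points. Two: 35.6 − 6.7 = 28.9 points.

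The 95% power stated in Section 11.2 plays no part here. Full enumeration of two-sided Fisher's exact test on the stated inputs gives 90.1%, which is a separate matter.

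**Step 3. Range for the unknown rate.** The protocol gives no rate of later rescue among week-16 responders. If a share f, equal in all arms, were reclassified, the planned difference becomes 35.6 × (1 − f).
- f = 5%: 33.8 points
- f = 10%: 32.0 points
- f = 20%: 28.5 points

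**Step 4. Could the conclusion change?** Two-sided Fisher, 30 per arm, placebo count unchanged.
- From planned counts of 12 vs 1 (p = 0.0011): 8 vs 1 gives p = 0.026 and 7 vs 1 gives p = 0.052, so five responders must be lost.
- From 12 vs 2 (p = 0.0048): 9 vs 2 gives p = 0.042 and 8 vs 2 gives p = 0.080, so four must be lost.

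Sections 1 and 3.3.1.1 report that Part A met its primary endpoint for both regimens with p-values below 0.0001. The counts are not given. Assuming 30 per arm and 0 to 3 placebo responders, start from the smallest dupilumab count that gives p < 0.0001 and go down to the largest that gives p > 0.05:

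| Placebo responders | Fisher: from → to (lost) | Unstratified Mantel-Haenszel: from → to (lost) |
|---|---|---|
| 0 | 13 → 5 (8) | 13 → 3 (10) |
| 1 | 15 → 7 (8) | 15 → 5 (10) |
| 2 | 17 → 8 (9) | 16 → 7 (9) |
| 3 | 18 → 10 (8) | 18 → 9 (9) |

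At least eight responders in one arm would have to be first rescued after week 16 and before the data cut.

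**The case against.** The strongest reply is that the conflict disappears when each sentence is read in context. The bullet defines the composite strategy as non-response after the event, and the Note beneath it says when that strategy applies. Rescue at week 30 then means non-response after week 30, and the week-16 result stands. The words about any time may simply keep rescue after stopping study drug under the composite rule. **This stands for the Note**, and is why the Note is called ambiguous here and not contradictory.

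For Section 8.3 the reply is weaker. Its opening words limit which analyses are meant, not when rescue occurs. The sentence before it does speak of double-blind and follow-up visits, so Part A rescue may be what was intended. But the sentence has no after-rescue qualifier, and the same section names the double-blind period when it means that period.

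A reader might go further and infer that rescue across the whole study, up to 172 weeks, can undo a week-16 response. The documents do not support that as a practical exposure. Part C was added by Amendment 4, in a protocol that already reports the Part A result, and Section 6.2 makes a completed Part A analysis final for the week-16 endpoints. The realistic exposure is Part B rescue before that data cut. Nor is there ground to infer that the reported result is false: reclassifying dupilumab responders shrinks the difference.

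The analysis plan, not shown, may set the rescue window. That would not remove the conflict, because the protocol states two rules rather than leaving one open.

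**Conclusion.** The point holds as a minor conflict in the rescue rule. Section 8.3, followed as written, gives a different week-16 status from the synopsis and the estimand bullet for one group only: week-16 responders first rescued after Part A. The Note is ambiguous and should be tightened with it.

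The true size is unknown because no later-rescue rate is given. It is 3.3 points per child at the planned 30 per arm, toward zero when the child is on dupilumab, where most responders are expected. On the assumptions in step 4, the reported significance would survive the loss of seven responders in either dupilumab arm. The estimate could move by a few points; the conclusion very probably would not. What stays open is which rule the reported estimate follows.

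**What to change.** Reconcile the synopsis, Section 8.3 and Section 11.4.3.1 to one analysis rule tied to the double-blind period, for example:

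> Patients who initiate rescue during Part A (before the first Part B dose, or by the end of the week 16 visit window if Part B is not entered) are non-responders at week 16, whatever the result of any pre-rescue biopsy. Rescue first initiated after Part A does not change week 16 status.

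Replace the references to the study as a whole in the Section 8.3 analysis sentence and in the Note accordingly. A cut-off at the week-16 assessment itself would not do. A child rescued in Part A is biopsied before rescue and skips the scheduled week-16 biopsy (Section 8.3; Table 1, footnote 2b), so a pre-rescue biopsy assigned to week 16 could then count as a response.

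Because Part A has been analysed, mark the change as a post-result clarification, state which rule was used, and report the number of week-16 responders first rescued after Part A and before the data cut.

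The cost is about one sentence in each of three sections, one statement of the rule applied, and one count from data already held. Only analysis wording changes, not clinical management. Section 8.3 counts emergency dilation as rescue while the estimand bullet names only corticosteroids; that is a separate point.

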## 11.4.3.2. Secondary Efficacy Analysis

Efficacy Endpoints at Week 16 (Part A)

Secondary efficacy endpoints that measure binary responses (eg, peak esophageal intraepithelial eosinophil count <15 eos/hpf) will be analyzed in the same fashion as the primary endpoint.

Continuous secondary efficacy endpoints will be analyzed using an analysis of covariance (ANCOVA) model for the FAS with treatment group, randomization stratification factor, and relevant baseline measurement as a covariate included in the model.

Regeneron Pharmaceuticals, Inc.
To account for use of rescue treatment, data will be set to missing for all time points subsequent to the use of rescue treatment.

For continuous efficacy data that are scheduled to be measured repeatedly post-baseline up to week 16 (eg, change in the proportion of days with 1 or more EoE signs from baseline to week 16 as measured by PESQ-C), missing data will be imputed by the pattern-mixture approach. Specifically, the WOCF-Multiple Imputation (WOCF-MI) approach, where the WOCF approach will be used for the missing data due to rescue treatment/AE/lack of efficacy and the MI approach will be used for the missing due to other reasons.

For continuous efficacy data that are scheduled to be measured only once post-baseline up to week 16, missing values at week 16 will be imputed with patient's baseline value or the available post-baseline value, whichever is worse, ie, a WOCF approach.

The primary analysis of EoE-EREFS will be based on centralized readings.

For transcriptome endpoints, the Wilcoxon rank-sum test will be used to test if the difference in median NES of the relative change from baseline to week 16 between the dupilumab and placebo groups is statistically significant. P-values will be reported.

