## 8.6. Method of Treatment Assignment

In Part A, approximately 90 patients will be randomized in a 1:1:1 ratio to receive higher or lower exposure dose arms of dupilumab (dose regimen according to the weight tier described in Section 8.1) or placebo according to a central randomization scheme provided by an IVRS/IWRS to the designated study pharmacist (or qualified designee). Randomization will be stratified according to weight at baseline ( $\geq$ 5 kg to <15 kg,  $\geq$ 15 kg to <30 kg, or  $\geq$ 30 kg to <60 kg).

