# **11.2.** Justification of Sample Size

The planned sample size is a total of approximately 90 patients (1:1:1 ratio, 30 patients in the higher dupilumab exposure group, 30 patients in the lower dupilumab exposure group, and 30 patients in the placebo group). See Section 3.2.2 for dose selection rationale.

The assumptions used in sample size calculation were based on Part A of the R668-EE-1774 study (a phase 3 study for adults and adolescents with EoE) and R668-EE-1324 (a phase 2 study for adults with EoE). In Part A of the R668-EE-1774, the proportions of patients achieving a peak esophageal intraepithelial eosinophil count of ≤6 eos/hpf at week 24 were 59.5% and 5.1% for dupilumab and placebo, respectively. In Part A of the R668-EE-1774, the proportions of adolescent patients achieving peak esophageal intraepithelial eosinophil count of  $\leq 6 \text{ eos/hpf}$  at week 24 were 36.4% and 0% for dupilumab and placebo, respectively. The treatment group difference observed in adolescents was approximately 36.5%. In the R668-EE-1324 study, the proportions of patients achieving histologic response at week 12 were 65% and 0% for dupilumab and placebo, respectively. The efficacy of dupilumab can be established as early as week 12. Based upon the similarity of pathophysiology and expected similarity of response between adults and pediatric patients, a similar proportion of responders at week 16 was assumed for sample size calculation. The lower exposure dupilumab group is assumed to have a similar treatment effect to the higher exposure dupilumab group. The treatment group difference observed in the R668-EE-1774 Part A adolescents was assumed for the sample size calculation for this study in children aged  $\geq 1$  year to < 12 years. It is estimated that with a total number of 90 patients (30 patients in the higher exposure dupilumab group, 30 patients in the lower exposure dupilumab group, and 30 patients in the placebo group), at the 2-sided 5% significance level using Fisher's exact test, the study can provide 95% power to detect a treatment difference of 35.6% in the proportion of

Regeneron Pharmaceuticals, Inc.

histologic responders (ie, patients achieving peak esophageal intraepithelial eosinophil count  $\leq 6 \operatorname{eos/hpf}$ ) at week 16 between placebo (5.1%) and each dupilumab treatment group (40.7%).

Sample size calculations were made using nQuery Advisor 7.0.

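### The transcriptome (NES) endpoints are tested with an unstratified Wilcoxon rank-sum test although randomisation is stratified by weight; the test is valid but loses power if weight group predicts NES change

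*Protocol*

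**What the plan says.** Section 8.6: "Randomization will be stratified according to weight at baseline", in three tiers (5 to under 15 kg, 15 to under 30 kg, 30 to under 60 kg).

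The Part A efficacy tests treat this factor as follows:

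- **Primary endpoint** (Section 11.4.3.1): a CMH "test adjusting for the randomization stratification factor (baseline weight group) will be utilized". On small strata: "The randomization stratification of baseline weight group may be pooled to ensure the sufficient sample size of each stratum".
- **Binary secondary endpoints** (Section 11.4.3.2): these "will be analyzed in the same fashion as the primary endpoint", so they are adjusted too.
- **Continuous secondary endpoints** (Section 11.4.3.2): ANCOVA "with treatment group, randomization stratification factor, and relevant baseline measurement as a covariate included in the model".
- **Transcriptome endpoints** (Section 11.4.3.2): "the Wilcoxon rank-sum test will be used to test if the difference in median NES" of the relative change from baseline to week 16 is significant, with p-values reported. No stratum or covariate is named, and no reason is given for the difference.

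Section 4.1.2 lists two such NES endpoints at week 16, for the EoE diagnostic panel and the type 2 inflammation signature. The only other unadjusted test in the statistical section is the planning calculation in Section 11.2, "at the 2-sided 5% significance level using Fisher's exact test", which is not an analysis of trial data.

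**The concern.** Stratified randomisation balances the arms within weight group, so differences between weight groups largely cancel out of the treatment comparison. The ordinary rank-sum test does not use this. Its null variance is that of a completely randomised trial and includes the spread between strata. If NES change differs by weight group, that variance is too large, the true size falls below 5% and power falls with it.

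At stake is efficiency on two secondary endpoints in a small trial, and consistency with the rest of the Part A plan. The protocol itself names the test, so this is not a detail left open for the SAP.

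A smaller point is that the text calls the procedure a test of a difference in medians. The rank-sum test compares distributions. It concerns medians only under an added shift assumption, which the text does not state.

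**Working it through.** **The plan's own figure.** There is none. The protocol states no power, effect size or variance for NES. Its sample-size statement concerns the primary endpoint only and has no bearing here.

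**Inputs from the protocol.** Three weight strata (Section 8.6); 30 patients per arm ("30 patients in the lower exposure dupilumab group, and 30 patients in the placebo group", Section 11.2); two-sided 5% level.

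**Assumptions, because the protocol gives no values.** Strata of 6/15/9 per arm, balanced between arms; normal outcomes with within-stratum SD of 1; stratum means of −g, 0 and +g, where g is the gap between adjacent strata; treatment shift of 0.8 SD.

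**Test statistics.**
- Rank-sum: z = (W − n(2n+1)/2) / √(n²(2n+1)/12). With n = 30 the null mean is 915 and the null variance is 900 × 61/12 = 4575, whatever the strata look like.
- Van Elteren: z = Σ c_k(W_k − n_k(N_k+1)/2) / √(Σ c_k² n_k²(N_k+1)/12), with N_k = 2n_k and c_k = 1/(N_k+1). Ranks are taken within each stratum.

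**Approximate size by hand.** The stratum means have average g(9 − 6)/30 = 0.1g, so their variance is B = g²(6 + 9)/30 − (0.1g)² = 0.49g². Treating ranks like the raw values, the unstratified test rejects only when the correctly scaled statistic exceeds 1.96√(1 + B):
- g = 0.5: B = 0.1225, threshold 2.077, size about 3.8%
- g = 1.0: B = 0.49, threshold 2.392, size about 1.7%
- g = 1.5: B = 1.1025, threshold 2.842, size about 0.4%

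**Simulation with the same inputs** (8,000 to 20,000 trials per setting):

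| Gap g (SD) | Size, rank-sum | Size, van Elteren | Power, rank-sum | Power, van Elteren | Effect of stratifying |
|---|---|---|---|---|---|
| 0 | 4.9% | 4.9% | 84.5% | 83.1% | −1.4 points |
| 0.25 | 4.6% | 5.1% | 83.3% | 82.6% | −0.7 |
| 0.5 | 3.6% | 4.9% | 81.4% | 83.2% | +1.8 |
| 1.0 | 1.8% | 4.8% | 70% | 83% | +13 |
| 1.5 | 0.5% | 4.8% | 52% | 83% | +31 |

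The simulated sizes agree with the hand approximation. The rank-sum size never rises above 5%.

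**Sensitivity to the assumptions.**
- With a 0.75 SD shift and splits of 4/15/11, 10/10/10 and 2/16/12, stratifying gains about 1 to 5 points at a gap of 0.5 SD and about 9 to 21 points at 1.0 SD.
- With a larger effect of 1.2 SD and the 6/15/9 split, both tests have about 99% power at a gap of 0.5 SD. At 1.0 SD the figures are 97.8% and 99.2%, so little is lost.

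**The case against.** The strongest reply is that nothing here is invalid. The rank-sum test holds its level, and the protocol may use a different valid test for a different kind of endpoint. The large losses need steps of 1.0 to 1.5 SD between adjacent tiers, which is 2 to 3 SD from the lightest to the heaviest group, and the protocol offers no evidence of this. Some of its text points the other way:

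- The endpoint is a within-patient relative change.
- The weight tiers are meant to give similar exposure (Section 3.2.2).
- The disease is described as having the same pathogenesis across ages (Section 1).
- Dupilumab clearly moved these signatures in the phase 2 study (Section 9.2.6.2), so power may be ample.

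Most of this stands. It limits the size of the point but does not remove it. None of it shows that weight is irrelevant, and the sponsor chose weight as the stratification factor and adjusts for it in the other specified Part A efficacy tests. Small strata are no obstacle, because pooling is already allowed.

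A reader might infer three stronger things that the documents do not support:

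- **That the NES p-values are too large.** This holds only if weight group predicts NES change; at a gap of zero there is no conservatism.
- **That the reference to medians produces a wrong result.** Under a location shift the test does address the difference in medians, and rewording changes no p-value.
- **That the week 16 test should simply be replaced.** Sections 1 and 3.3.1.1 report that Part A has already met its primary endpoint, so a silent replacement would be a change of test after results were known.

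Only selected secondary endpoints enter the testing hierarchy, and their order is left to the SAP. Whether an NES endpoint carries a confirmatory claim is therefore unknown.

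**Conclusion.** The point holds as one of efficiency and consistency, not validity. The protocol fixes an unstratified rank test for the NES endpoints after weight-stratified randomisation, without giving a reason, while the other specified Part A efficacy tests adjust for weight group. Type I error is not inflated.

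Under the assumed 6/15/9 split and 0.8 SD effect, the consequence runs from a slight advantage for the unstratified test (gaps up to 0.25 SD) to a loss of about 2 points of power at 0.5 SD and about 13 at 1.0 SD. The association between weight group and NES change, the stratum sizes and the NES effect are all assumptions, so the true loss cannot be placed within that range. The case for changing is that the protection costs very little, not that a large loss has been shown.

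**What to change.** In Section 11.4.3.2, and correspondingly in the SAP:

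1. Specify a van Elteren test stratified by baseline weight group, with groups pooled as Section 11.4.3.1 already allows.
2. Report a stratified Hodges-Lehmann shift estimate with its 95% confidence interval beside the p-value.
3. Describe the test as one of a shift in distribution.
4. Keep the prespecified rank-sum result at week 16 and present the stratified analysis beside it as a labelled sensitivity analysis, stating that it was added after Part A results were known.

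This takes a few sentences and some standard programming, and needs no new data. The statistical cost is about 1 to 1.5 points of power for the stratified test if weight is unrelated to NES change.
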